### 5.0 Study Procedures

#### 5.1 Study Design

##### 5.1.1 Overview

This study represents Steps 4 and 5/6 of the QUERI Process, which are also described under "Implementation Trial with Evaluation" in the new Research/Implementation Pipeline used for the most recent QUERI Annual Reports (Appendix 1 to this protocol). Specifically, this will be a hybrid 1 effectiveness trial conducted under real-world implementation conditions in multiple sites and regions. The focus is on assessing the impacts of the program on patient outcomes (research aims 1-2), as well as optimization of the implementation strategy (aim 3).

This project is being conducted at five VA facilities (including eight clinics) implementing SMAs as part of usual care. These sites have been selected because they are interested in implementing P2P groups as an add-on to the SMAs as part of usual care. As these programs are starting, resources at each site do not permit all eligible patients to receive these two new programs. Therefore there are three groups being studied, all receiving usual care for their facilities: (1) usual care without SMAs, (2) usual care with SMAs, and (3) usual care with SMAs and P2P.

The study design is a multi-site, modified cluster randomized controlled design. Our first analysis is a comparison of two active treatment arms, one involving SMA and the second involving SMA+P2P. Some sites may only conduct one group at a time depending on variability of their resources over time, but all sites will conduct a number of groups over the study period and the two

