treatments will be offered in a random sequence within site, providing the clusterized random assignment required for comparability of the two treatment arms. In a modification of the classical cluster randomized design, patients are not assigned to groups prior to the group randomization to treatment but are recruited from a population of eligible patients when the site is ready to run a new group. If patients are then selected differentially into the groups we will lose all the advantages of the randomization step. Thus patients will be randomly sampled for invitation from eligible patients and recruited for each wave of the group treatment with a standard script that is identical whether the group is SMA only or whether P2P will be offered as an additional optional part of the intervention. All invited patients will be told that they are being invited to participate in SMAs, provided a brief description of what the SMAs involve, and informed that some groups will also be offered an additional (optional) opportunity to participate in P2P as a supplement to the SMAs. All invited patients will also be told that they are being offered an additional (optional) opportunity to participate in this research study. Participation in the research study is not required to participate in the SMAs or SMAs + P2P.

The study population will consist of diabetes patients who have poor glycemic control. Because not all eligible patients will be able to be invited to participate in one of the two programs during the study period, we will also have a pool of eligible patients whom we can use for untreated controls. We will randomly pull a sample of patients from each site to serve in this group. Thus, the trial will compare outcomes across three different treatment groups: (1) usual care without SMAs, (2) SMAs; and (3) SMAs + P2P.

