## **5.6 Data Analysis**

This will be an effectiveness trial conducted under real-world implementation conditions in multiple sites and regions. The focus is on assessing the impacts of the P2P program on patient outcomes as well as optimization of the implementation strategy.

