### **5.6.1 Analysis Plans by Aim**

Aim 1 (Evaluation of the effect of SMAs and SMAs+P2P compared to usual care on diabetes patients' glycemic control, blood pressure, statin use, and insulin starts at 6 and 12-18 months post-enrollment): The primary analysis will be an intention to treat analysis (ITT) comparing all participants scheduled for an SMA (regardless of whether an SMA was actually attended) and eligible patients randomized to usual care. We also will conduct analyses comparing outcomes between the usual care group and: 1) The SMA Attendee group, defined as a subset of those in the SMA ITT group who attended at least one SMA; and 2) the SMA Engagement group, defined as the subset of patients who attended at least half of the SMAs offered in the series.

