Aim 2 (Assessment of the impact of SMAs and SMAs+P2P on service utilization and patient-centered outcomes, including patients' satisfaction with VA care, diabetes-specific quality of life and social support at 6 and 12 months post-enrollment). In our analysis of changes in patient-centered outcomes as reported on patient surveys, we will conduct a paired Wilcoxon signed rank test to determine if there are significant changes between baseline and the 6- and 12-month post-enrollment evaluation periods. We will use the Benjamini-Hochberg (BH) procedure to attempt to control the false discovery rate due to the multiple comparisons. There were very few participants in the SMA+P2P group chose to be formally matched with another participant in their SMA to give and receive peer support outside the SMA. If we do not have sufficient sample size of participants in P2P, we will be unable to compare outcomes between the SMA-only and SMA+P2P arms. In that case, will only conduct our primary analysis that combines the two SMA groups (SMA-only and SMA+P2P) into one active treatment group and compare clinical outcomes of participants participating in SMAs with those in usual care.

Fidelity of the P2P Program. To collect data on fidelity, checklists of key content areas to cover and communication skills that should be used will be completed and forwarded to Ann Arbor. A HBC or another qualified health behaviorist will attend the first P2P visit (immediately following the first SMA) and will complete a fidelity assessment checklist. Additionally, they will provide feedback to the P2P facilitator immediately following the session. This feedback will be documented and shared with the Ann Arbor study team. An assessor will continue to attend drop-in sessions, completing fidelity assessments and providing feedback, until he/she feels the P2P facilitator is ready to continue without assistance. Then the fidelity assessments will be completed approximately every 3rd drop-in session for the remainder of the study. Additionally, the P2P facilitators will be asked to complete self-assessment checklists after each session which will be forwarded to Ann Arbor.

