### 5.6.2 Sample Size and Power Calculations

We chose five VA health systems (8 sites, as one healthy system will implement the program in 4 separate sites within the system) in which to implement SMAs + P2P based on our estimation of feasibility of implementation, given budget and time constraints. This number of health systems should also provide some variability in terms of the CFIR constructs (especially implementation context), which is important for investigating the role of these constructs in implementation success. We want to ensure that the study has a sample size sufficient to detect a clinically meaningful decline in A1c of 0.5% or a SBP decline of 5mm Hg between SMA and SMA+P2P. Based on discussions with clinical managers at a number of sites, both in relation to this project and others, they would be unlikely to undertake an addition of a new clinical management strategy unless it offered a benefit of this magnitude.

The clustering induced by the treatment in small groups requires that we account for the intra-class correlation within clusters in our sample size calculation. An increasing number of publications have started to provide estimates of ICCs from practice-based interventions. However, there are not good sources for estimates of ICCs of clinical intermediate outcomes induced by shared medical appointments. In a previous RCT conducted by us of P2P alone, which given the intimate nature of the pairing may represent an upper limit of induced correlation that might be found in a larger SMA, we found that the ICC was estimated at 0.10 but it was not significantly different from 0. Thus we used a range of 0 to 0.10 for the estimate of ICC of the outcome a1c or SBP measurement.

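### The arm comparison that the design randomises (SMA vs SMA+P2P) is called first in 5.1.1, but 5.6.1 makes it conditional on P2P uptake and gives it no A1c or SBP model

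*Combined protocol and SAP*

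**What the plan says.** All references are to the combined protocol and SAP.

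- **5.1.1 Overview** gives the lead place to the two active arms: "Our first analysis is a comparison of two active treatment arms, one involving SMA and the second involving SMA+P2P". The two group types run in random order within each site, which is described as "providing the clusterized random assignment required for comparability of the two treatment arms".
- **5.6.2 Sample Size and Power Calculations** opens by asking for a "sample size sufficient to detect a clinically meaningful decline in A1c of 0.5% or a SBP decline of 5mm Hg between SMA and SMA+P2P". It later gives power for both active groups against inactive controls as well.
- **5.6.1, Aim 1**, names a different main analysis: "The primary analysis will be an intention to treat analysis (ITT) comparing all participants scheduled for an SMA", attended or not, with usual-care patients.
- **5.6.1, Aim 2**, confirms that this pools the arms, referring to "our primary analysis that combines the two SMA groups (SMA-only and SMA+P2P) into one active treatment group". It reports that very few patients in SMA+P2P chose to be paired. If P2P numbers prove too small, it says, "we will be unable to compare outcomes between the SMA-only and SMA+P2P arms", and only the pooled analysis is run. No number or decision time is given.
- **The A1c model in 5.6.1** has one treatment indicator, under an aim framed against usual care, with random intercepts for patient and site. The SBP analysis is identical.

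**The concern.** The contrasts ask different questions on different evidence. SMA vs SMA+P2P compares patients whose group type came from a random sequence, recruited with one script. Referrals were booked by a scheduler unaware of which groups would offer P2P (5.2). Pooled SMA vs usual care compares patients who were referred or accepted an invitation with a random sample of patients not invited (5.1.1, 5.2), although 5.6.1 calls the controls randomised. The arm comparison is therefore the one that the described random assignment protects.

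That comparison has the weakest standing in the analysis section. A reader of 5.1.1 and the opening of 5.6.2 expects it to lead. A reader of 5.6.1 finds it conditional on an undefined amount of uptake, to be judged with uptake known, and without a model. The randomised result could then go unreported, or be produced with a model chosen after the data are seen. The obvious model to borrow omits the unit that was randomised.

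**Working it through.** **1. The passages side by side**

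| Section | Leading contrast | Status given |
|---|---|---|
| 5.1.1 | SMA vs SMA+P2P | first; randomised by group |
| 5.6.2, opening | SMA vs SMA+P2P | lead target effect |
| 5.6.2, later | both, in turn | power stated for each |
| 5.6.1, Aim 1 | pooled SMA vs usual care | primary |
| 5.6.1, Aim 2 | pooled SMA vs usual care | primary; arm comparison only if P2P numbers allow |

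**2. Inputs**

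From 5.6.2: SD of A1c change 1.45; target 0.5%; ICC 0 to 0.10; 10 to 16 groups per site, split equally between arms; 8 to 14 people per group; minimum 560 active and 560 control. Alpha is not stated, so two-sided 0.05 is assumed.

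**3. The plan's own power statement**

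Variance of an arm mean = SD² × (1 + (m − 1) × ICC) / (k × m), for k groups of size m, with Satterthwaite degrees of freedom and a noncentral t. With 5 sites, k = 25 per arm. At ICC 0.10, power is 0.782 for m = 10, 0.815 for m = 12 and 0.838 for m = 14. At m = 10 and ICC 0.05 it is 0.88. This reproduces the plan's claim of 0.8 power except at group size 10 with ICC 0.1.

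The stated totals imply a different number of sites: 7 × 10 × 8 = 560 and 7 × 16 × 14 = 1,568. The text counts 8 sites, which would give 8 × 10 × 8 = 640 and 8 × 16 × 14 = 1,792. A range over sites is therefore shown below.

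**4. Power for 0.5% A1c (m = 8, ICC 0.10, normal approximation)**

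Design effect = 1 + 7 × 0.10 = 1.7.

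- SMA vs SMA+P2P, 5 sites (25 × 8 = 200 per arm): SE = 1.45 × √(2 × 1.7 / 200) = 0.189; 0.5 / 0.189 = 2.64; power = Φ(2.64 − 1.96) ≈ 0.75.
- SMA vs SMA+P2P, 7 sites (35 × 8 = 280 per arm): SE = 1.45 × √(2 × 1.7 / 280) = 0.160; 0.5 / 0.160 = 3.13; power = Φ(3.13 − 1.96) ≈ 0.88.
- Pooled, 560 vs 560, controls unclustered: SE = 1.45 × √(1.7 / 560 + 1 / 560) = 0.101; power above 0.99.

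Satterthwaite degrees of freedom lower the two arm figures slightly, to 0.736 and 0.870.

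**5. Borrowing the A1c model for the arm comparison**

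Group type varies within site, so a site intercept does not absorb variation between SMA groups. If the ICC is 0.10 and the model ignores it, the true two-sided error at nominal 0.05 is 2 × (1 − Φ(1.96 / √design effect)).

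- m = 8: design effect 1.7; 1.96 / √1.7 = 1.50; error ≈ 0.13.
- m = 14: design effect 2.3; 1.96 / √2.3 = 1.29; error ≈ 0.20.

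**6. Does low uptake prevent the comparison?**

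By type of group scheduled, the number analysed depends on the groups run and the patients scheduled, not on pairing. The SE in step 4 does not change; the expected effect does. As an illustration, suppose that P2P works only through pairing and lowers A1c by 0.5% in those paired. At half uptake the scheduled-group effect is 0.25%, and with 7 sites power falls to Φ(0.25 / 0.160 − 1.96) ≈ 0.35. The 95% interval is still about ±1.96 × 0.160 = ±0.31%.

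**The case against.** The strongest reply is that 5.6.1 already settles the matter. Only that section uses the word primary for a comparison, it does so twice, and the two uses agree. Being first in 5.1.1 may mean order rather than rank. The abstract, the objectives and Aim 1 all take usual care as comparator. This stands: a reader might infer that nothing ranks the contrasts and that either could be reported as the planned main result, but the Aim 2 text puts the pooled contrast first.

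Three other inferences also go too far.

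- The focus sentence in 5.6, "The focus is on assessing the impacts of the P2P program on patient outcomes", might be read as making SMA vs SMA+P2P the main comparison. It names no comparator.
- The sample size might be thought to belong only to the arm comparison. Section 5.6.2 states power for both contrasts.
- Two main tests at 0.05 would give 1 − 0.95² = 9.75% chance of at least one false positive. That requires both to be declared main results at an assumed 0.05, and the plan calls only one primary.

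The sponsor could add that, with very few pairs, the arm comparison says little about the effect of being paired. That is fair, and step 6 shows the loss of power. It is a reason for cautious interpretation, not for omission: the effect of offering P2P to a group can still be estimated under the plan's own rule of analysing patients as scheduled. None of these replies reconciles 5.1.1 and the opening of 5.6.2 with 5.6.1, defines enough uptake, or supplies the missing model.

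**Conclusion.** The concern holds in a limited form. The plan has a primary analysis, pooled SMA vs usual care, but 5.1.1 and the lead target in 5.6.2 have not been brought into line with it. The contrast randomised by group has no A1c or SBP model, and an undefined uptake condition, written with low pairing already known, could needlessly discard it.

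Power for the arm comparison at groups of 8 is about 0.75 (5 sites) to 0.88 (7 sites), so neither figure should be quoted alone. The pooled contrast exceeds 0.99 with 560 controls. Borrowing the existing A1c model would give a true error of about 0.13 to 0.20. These figures assume two-sided alpha 0.05, SD 1.45 and ICC at the plan's upper value of 0.10. At a lower ICC, power is higher and the error inflation smaller; at ICC 0 there is no inflation.

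**What to change.** 1. Keep pooled SMA vs usual care on A1c as primary. Reword the sentence in 5.1.1 that puts the two active arms first, and the lead target contrast in 5.6.2, to match. Power for each contrast is already given in 5.6.2, so only label which belongs to the primary and which to the secondary.
2. In 5.6.1, name SMA+P2P vs SMA-only on A1c and SBP, by type of group scheduled, as a secondary analysis that is always reported as an estimate with its interval. Use the existing mixed model with an SMA+P2P indicator and a random intercept for SMA group within site.
3. Replace the uptake condition under Aim 2 with this rule, and note that low uptake dilutes the effect but does not prevent the comparison.
4. If a formal test of the secondary is wanted, state its alpha and its place in the order. Testing it only after a significant primary is one acceptable option.

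The cost is wording changes in 5.1.1, 5.6.1 and 5.6.2 and one extra model per outcome on data already collected. No patient procedure or sample size changes. The downside is that SMA vs SMA+P2P becomes explicitly secondary, and its interval is wider once SMA group is modelled.

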### **5.1.2 Risks**

#### ***VA Patients***

Participants will be instructed to skip any survey or interview question they feel uncomfortable answering. Participants may also end an interview at any time. Participants will be told that they may withdraw from the study at any time without penalty. If a potential study participant does need support or wants further clarification of any issue, a study investigator will address the concern in a sensitive and professional manner (i.e., by calling the participant directly and/or recommending follow up with his primary care provider).

We believe that risk of a breach of confidentiality is low. Throughout the study, IRB and HIPAA guidelines will be followed to ensure the privacy and integrity of the information we collect. To minimize the risk of a breach of confidentiality, we will perform the following steps. First, as soon as the cohort is defined by the data manager, each patient in the cohort will be assigned a unique study ID. All electronic data, including audio recordings, will be stored in an access-restricted folder on the HSR&D drive, which resides behind the VA firewall. All identifying data (e.g., names of other patients, providers, facilities) will be removed from transcripts of the audiofiles during the transcription process. At the study's conclusion, all personally identifying information (PII) will be moved to an access restricted folder on the Ann Arbor VA OI&T network, accessible only to the HSR&D data manager. Members of the study team will no longer have access to these data. Data will be destroyed by the data manager 6 years following the end of the fiscal year after completion of the research project. All research data will be presented in aggregate form only. The data manager will also be responsible for creating analytic datasets for statisticians and investigators; these datasets will be de-identified per HIPAA guidelines. Furthermore, study staff members sign a pledge of confidentiality and understand that breach of confidentiality is grounds for dismissal. Study staff members are required to complete annual training on privacy and HIPAA, as well as biannual training on human subjects protection. All research findings will be presented in aggregate only.

#### ***Minimization of risk to usual care***

A number of steps will be taken to ensure the safety and confidentiality of patients who participate in the P2P program. All patients participating in P2P will receive training for the peer support component of the study in order to prepare them for those interactions. Patients' confidentiality will be protected via several mechanisms. Patients who are comfortable doing so will be asked to provide their name and phone number to their partner. All patients will be advised to not give out their address or other personal information. This will be explained to the participants during the initial face-to-face group visit, and on the "Do's and Don'ts" card given to the participants to help guide the peer support calls. Finally, messages left on participants' answering machines will not reference any information about their diabetes or other health problems.

#### ***VA Employees***

There are no physical or psychological risks to study participation. The social/legal: risk to these

participants is potential loss of confidentiality from their interview responses and observational data (Ann Arbor only). The interviews will include questions about various characteristics of the VA medical center where they work, and respondents may provide negative comments about the organization. Linking these responses to a particular employee could result in adverse actions against that employee by other members of the organization, including the employee's supervisor.

Ann Arbor study staff will recruit the employees for all participating sites to reduce the risk of a breach of confidentiality. The same precautions for protecting the audiofiles and transcripts of Veteran participants will be used for protecting these data, along with observation notes, from VA employees. Data will be stored behind the VA firewall at the VAAAHS and minimal Ann Arbor study staff members will have access.

### **VA Patients and VA employees**

There is no direct benefit to patients or VA employees as a result of participation. Patients may benefit indirectly, as this study may result in improvement in diabetes care at the VA. Findings from the study should provide information that will help with implementation of the P2P program, to facilitate its integration into existing clinic structures and processes and reduce the effort required by employees to implement and maintain the program.

The study team will meet regularly during the recruitment period. These meetings will include discussion of the events of the week, particularly any problems/events that have come up. The PI and study team will work to address any problems/events to reduce the likelihood of occurrence in the future, to keep the risk to subjects as low as possible, and to maximize the potential study benefits. The research team will visit the sites in year 2 (approximately six months following implementation) to conduct an on-site assessment of program status, interview key staff members, and to problem-solve any issues that have come up.

#### **5.1.3 Study Population**

##### **VA Patients**

We will enroll up to 1,100 VA patients to the SMA and SMA+P2P groups and 1,100 VA patients to the control group. Inclusion criteria are reflective of the criteria to participate in SMAs and P2P, with the addition of criteria to insure informed consent. Please see section 5.4 for a complete list of these criteria.

##### **VA Employees**

We will enroll up to 56 VA employees for the pre-, mid-, and post-implementation interviews. VA Employees will be asked to participate based on their role in the SMA and/or P2P programs. The director of primary care, clinicians participating in the SMAs, the P2P group facilitators, and other key staff involved in diabetes patient care (e.g., nurses, dieticians, pharmacists) will be asked to participate in semi-structured interviews. These employees, who may play a role in the SMA or P2P program (as a referring provider, or as someone facilitating the SMA or P2P group visits), will be targeted to obtain information on CFIR (Consolidated Framework for Implementation Research) constructs likely to influence implementation success. Additionally, in Ann Arbor, we will enroll up to an additional 25 VA employees in the sustainment assessments (i.e., interviews, meeting observations, SMA observations). Employees will be asked to participate based on the teamlets who will be conducting upcoming SMAs. All members of the involved teamlets (e.g., MD, PharmD, RD, RN, LPN, MSA, etc.) will be asked to participate in the sustainment assessments.

